1.2 Rationale for Exploratory/Translational Testing

1.2.1 HPV DNA Testing

High-risk HPV types have been implicated in the etiology of cervical cancer (28-30), and its precursor, high-grade cervical intraepithelial neoplasia (CIN) (29,31); and anal cancer (32-33) and its putative precursor, high-grade anal intraepithelial neoplasia (AIN) (34-37). More than 100 HPV types have been identified, which by definition differ from one another by at least 10% of their DNA sequences (38). Of the HPV types conferring the highest risk for high-grade disease and invasive cancer, HPV types 16 and 18 are the most common (32,38), with HPV 16 infection being the single most common HPV type in anogenital cancer (39).

However, it is not known if the distribution of HPV types in cervical cancer developing in HIV-infected is different from that developing in HIV-uninfected women, where it has clearly been shown that HPV 16 and 18 are present in approximately 50% and 20% of cancers, respectively. We will also collect cervical and anal swabs at baseline prior to initiation of therapy, and at completion or premature discontinuation of therapy. The post-treatment samples will allow us to examine in an exploratory analysis, the effect of treatment on HPV persistence, and determine whether HPV persistence is related to disease recurrence. We also propose to study anal samples for HPV DNA at these time points. Studies have shown a relationship between cervical and anal cancer, and little is known about anal HPV in women with cervical cancer. We can also examine the effect of cervical cancer treatment on anal HPV persistence.

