Therapy for cervix cancer has changed over the last decade. Chemotherapy has been shown to be beneficial and has been added to our armamentarium of surgery and radiation. Nevertheless, in an era of personalized medicine, the potential biological differences of cervix cancer associated with different HPV types and host variation have not been adequately evaluated as determinants of cervix cancer outcome and/or response to therapy. Prior studies were conducted in the era of radiation alone, not concomitant chemoradiotherapy, and none address HIV-associated cervical cancer (40-42). Moreover, cervix cancer in an advanced state and in the setting of HIV has a poor prognosis. Since HPV types associated with cancer have divergent risks and associations with tumor types, we expect that knowledge of the HPV type will help to identify patients most at risk for treatment failure, recurrence, and response to surgery, radiation and/or chemotherapy.

Although detection of an oncogenic HPV type is associated with increased risk of anogenital cancer, recent studies of cervical lesions suggest that differences in the genome sequence within variants of a given HPV type, such as HPV 16, may substantially affect the level of risk. Thus, “European” or “prototype” variants of HPV 16 were associated with lower risk of CIN 2 or 3 and cervical cancer than were “non-European” or “non-prototype” variants (43). This was shown to be the case for AIN as well compared to “prototype” HPV 16 variants. MSM with anal “non-prototype” HPV 16 variants were more than three times as likely to develop AIN 3 (43-44). In a study by Palefsky et al., an elevated risk for AIN 2 or 3 was

associated with infection with G131 European variants of the HPV 16 E6 protein when compared with the prototype HPV 16 strain (44).

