1.2.3 HPV Serology

Antibodies to conformational epitopes on synthetically produced virus-like particles (VLPs), structurally similar to the HPV virion, have been shown to develop in response to HPV infection (62-65). Serologic responses directed at type-specific epitopes on VLPs are often detectable when there is clinical evidence of disease. Serologic titers can be quantified and related to clinical disease status (63, 65-66). In fact, it appears that higher titers might correlate with worsening grade CIN and cancer (67). Neither seropositivity nor antibody titers have been explored as a marker for persistence or recurrence in HIV-associated cervical cancer.

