2.3 Exploratory Objectives

2.3.1 To determine the 1-year progression-free survival (PFS) of HIV-infected women with locally-advanced invasive cervical cancer (LACC) Stage IB, II, III, and IVA who receive weekly cisplatin concomitant with radiotherapy and ART.

2.3.1.1 Determine PFS in all registered participants, regardless of completion (intent to treat-ITT)

2.3.1.2 Determine the PFS in the subset of participants who complete the prescribed chemotherapy/ radiotherapy

2.3.1.3 Compare PFS in these subjects with PFS of HIV-uninfected subjects as reported in the literature, stage for stage.

2.3.2 To describe the effects of treatment on participants' CD4 counts, HIV viral load and concurrent AIDS-defining conditions.

2.3.3 To describe cervical cancer recurrence patterns in HIV-infected participants with LACC defined as loco-regional and/or distant recurrences.

2.3.4 Determine 1-year overall survival and causes of death (i.e., cancer-related, HIV-related, or other).

2.3.5 To evaluate the effects of weekly cisplatin concomitant with radiotherapy on adherence to ART.

2.3.6 Collect serum and cervical and anal swab material for the following exploratory analyses:

2.3.6.1 To describe the distribution of HPV DNA types and HPV strain variants in cervical and anal swabs collected at baseline, prior to initiation of study treatment;

2.3.6.2 To assess the concordance between HPV DNA types and HPV strain variants detected in cervical and anal swabs collected at baseline, prior to initiation of study treatment;

2.3.6.3 To investigate the effect of study treatment on HPV persistence in cervical and anal swabs and its relationship to cervical cancer persistence or recurrence;

2.3.6.4 To describe the gene methylation profiles in cervical and anal swabs collected at baseline, prior to initiation of study treatment;

- 2.3.6.5 To investigate the relationship between baseline gene methylation profiles and cervical cancer persistence or recurrence;
- 2.3.6.6 To measure serum antibody titers to HPV 16 and HPV 18 at baseline and on study, and to determine whether baseline titers or changes during therapy correlate with cervical cancer persistence or recurrence.

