To determine the HPV DNA types and HPV strain variants present in cervical cancer and in the anus of cervical cancer patients, frequency tables of HPV DNA types and HPV strain variants will be constructed for cervical and anal samples at baseline, end of treatment and at recurrence (if applicable). The binomial proportion and its 95% confidence interval will be used to estimate the proportion of each HPV DNA type and each HPV strain variant that occurs in at least 5% of patients in cervical or anal specimens. Concordance between anal and cervical specimens with respect to detection of specific HPV DNA types and HPV strain variants will be assessed using McNemar's chi-square test.

Changes in HPV DNA types and strain variants between baseline and post-treatment measurements will be assessed using McNemar's chi-square test for each DNA type and

strain variant. Proportional hazards models and logistic regression models will be used to evaluate the association of change in DNA types with progression free survival and local control, respectively.

The binomial proportion and its 95% confidence interval will be used to estimate the proportion of patients who have abnormally methylated genes for each gene tested.

Gene methylation profiles will be summarized at baseline.

Concordance between gene methylation profiles between cervical and anal swabs will be assessed at baseline using the kappa statistic.

The chi-square test will be used to assess the association between baseline gene methylation profiles and cervical persistence or recurrence.

The logistic regression model will be used to assess the effects of HPV-16 and HPV-18 serologic titer levels with disease persistence or recurrence using the logarithmic transformation for the titer levels. Similarly, the effects of changes in HPV-16 and HPV-18 titer levels from baseline to treatment on outcome measures (progression free survival, local control) will be assessed using proportional hazards models and logistic regression models.

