CDH1	AATTTAGGTTAGAGGGTTATCGCGT	TCCCCAAAACGAAACTAACGAC
RARβ	AAGTAGTAGGAAGTGAGTTGTTAGA	CCAAATTCTCCTTCAAATAA
HIC1	GTTAGGCGGTTAGGGCGTC	CCGAACGCCCTCATCGTAT
TSLC1	GTGAGTGACGAAATTGTAATGTTGGTT	AATCTAACTTCTTACACCTTATTAAAA
RASSF1A	GCGTTGAAGTCGGGGTTC	CCCGTACTCGCTAACCTTAAACG
DAPK	GGATAGTCGGATCGAGTTAACGTC	CCCTCCCAAACGCCGA
FHIT	TTGGGGCGCGGGTTGGGTTTACGC	CGTAAACGACGCCGACCCACTA
PTEN	GGTTTTCGAGGCCTCG	CGCCTCACAAACGACTCAACT
p14^{ARF}	GTGTTAAAGGGCGGCGTAGC	AAAACCCCTCACTCGCGACGA
VHL	TGGAGGATTGCGTACGC	GAACCGAACGCCGCGAA
p73	GGACGTAGCGAAATCGGGTTTC	ACCCCGAACATCGACGTCCG
FANCF	TTTTGCGTTGGAGAACGTTTC	ATACACCGCAAACCGCCGACGAACAAACG
BRCA1	TCGTGGTAACGGAAAAGCGC	AAATCTCAACGAACTCACGCCG
TNFRSF10C	TTACCGTACGAATTAGTTAAC	ATCAACGACCGACCGAAACG
TNFRSF10D	GGGATAAAGCGTTCGATC	CGACAAACAAAACCGCG

SERUM SPECIMENS

HPV Serology

Serology to measure neutralizing antibodies against HPV 16 and HPV 18 will be performed using a pseudovirion (PsV)-based neutralizing assay (PBNA). HPV-16 and HPV-18 PsVs were

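### The HPV-16 and HPV-18 titer models in section 11.1 ignore the HPV type of the cancer, so a titer association cannot be told from a tumour-type association

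*Combined protocol and SAP*

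**What the plan says.** Appendix XI, under HPV Serology, describes the assay: "Serology to measure neutralizing antibodies against HPV 16 and HPV 18 will be performed using a pseudovirion (PsV)-based neutralizing assay (PBNA").

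The analysis sits in section 11.1. For titer levels: "The logistic regression model will be used to assess the effects of HPV-16 and HPV-18 serologic titer levels with disease persistence or recurrence", on the log scale. A second sentence covers "the effects of changes in HPV-16 and HPV-18 titer levels from baseline to treatment on outcome measures (progression free survival, local control"), using proportional hazards and logistic models. Neither sentence names a subset, covariate, stratum or interaction for HPV type. It is also not said whether the two titers enter one model or two.

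These models serve objective 2.3.6.6, which is exploratory and asks "to determine whether baseline titers or changes during therapy correlate with cervical cancer persistence or recurrence".

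Three other places bear on the point:

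- Section 1.2.3 on the serologic response: "Serologic responses directed at type-specific epitopes on VLPs are often detectable when there is clinical evidence of disease".
- Section 1.2.1 on HPV type: "we expect that knowledge of the HPV type will help to identify patients most at risk for treatment failure". Hypothesis 2.1.5 also expects baseline HPV types, and separately serology, to be associated with recurrence.
- Section 1.2.1 on type shares in HIV-uninfected women: "HPV 16 and 18 are present in approximately 50% and 20% of cancers, respectively". It says that the distribution in HIV-infected women is unknown.

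Baseline cervical type is measured in the same trial, and Appendix XI probes HPV 16 and HPV 18 individually. Section 11.1 analyses the type data separately and does not link them to the titers.

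**The concern.** A variable that is expected to be related both to the exposure (the titer) and to the outcome (failure) is measured but left out of the model. If women with an HPV-16 cancer tend to have higher HPV-16 titers, and HPV-16 cancers fail more or less often than others, an HPV-16 titer will appear prognostic when it carries nothing beyond type. The sign of the error follows the sign of the type effect.

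There is a second, conditional issue. If a titer matters mainly when the cancer carries the matching type, its effect is averaged with that of women in whom it is irrelevant.

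The introduction says the trial will inform, in a preliminary way, whether these measures are useful as markers. A reader of the results could not tell whether serology adds anything to HPV typing.

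**Working it through.** **Plan's own figure.** There is none for serology. The 38 evaluable women in section 11.2 are sized for treatment completion. I use 38 only as the number available.

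**Expected numbers by type** (shares from section 1.2.1, HIV-uninfected women):

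- HPV-16: 0.50 × 38 = 19
- HPV-18: 0.20 × 38 = 7.6, about 8
- Neither: 38 − 19 − 7.6 = 11.4, about 11

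About 50% of the women in the HPV-16 model, and 80% in the HPV-18 model, would have a cancer without that type.

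**False positives when the titer has no effect.** Only n and the type shares come from the documents; the rest is assumed.

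- log2 titer: SD 2, with mean higher by 2 (4-fold) or 4 (16-fold) in women with the matching cancer.
- logit P(failure) = b0 + ln(OR) × [HPV-16 cancer], with b0 set so that 40% fail overall.
- Likelihood-ratio test of the HPV-16 titer at two-sided 0.05, about 2,000 simulated trials per setting.

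To show what the odds ratios mean: for OR 0.33, failure risks of 53% and 27% fit, since 0.53/0.47 × 0.33 = 0.37 in odds, or 27%, and (53 + 27)/2 = 40. For OR 0.5 the risks are about 48% and 32%.

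| Type OR | Own-type titer shift | Planned model rejects | Adjusted for type |
|---|---|---|---|
| 0.33 | 16-fold | 21–25% | 6–7% |
| 0.33 | 4-fold | 12–14% | 6–7% |
| 0.5 | 4-fold | about 8.5% (7.8–9%) | about 6% (6–7%) |
| 0.67 | 4-fold | no visible difference | |

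Ranges are over independent runs. Entering both titers jointly does not cure the problem: at OR 0.33 it rejects in 13% (4-fold) and 19% (16-fold).

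**Direction of the bias.** A large-sample calculation used a different titer model (assumed: seropositive in 60% of matched and 20% of unmatched women, event risk about 35%). With no titer effect and an HPV-16 cancer OR of 0.5, the all-women HPV-16 titer OR per doubling is 0.91. With an HPV-18 cancer OR of 2 as well, the two titer ORs are 0.88 and 1.12. All return to 1.00 after adjustment.

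**Dilution, only if the titer acts in matching cancers alone.** In the same model, a true OR of 1.5 in matched women appears as 1.25 (HPV-16) and 1.12 (HPV-18) in all women. Adjustment for type barely helps (1.29 and 1.13); analysis within the matching type recovers about 1.5. If instead both titers act equally in all women, a joint model gives 1.50 and 1.50, so nothing is diluted.

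**Power** (first simulation; log-odds 0.5 per doubling):

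| Truth | Planned | Adjusted for type | Own-type model only |
|---|---|---|---|
| Titer acts only for matching type | 0.23–0.24 | 0.28–0.29 | 0.61–0.62 (actual size about 0.07) |
| HPV-16 titer acts in all women, unrelated to type | 0.76–0.79 | about 0.77–0.78 | 0.34–0.38 |
| HPV-16 titer acts in all women and tracks type | 0.83 | 0.72 | about 0.34 |

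The own-type model relates each woman's titer against her own cervical type to outcome in about 19 + 8 = 27 women.

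These runs cover the logistic model for titer level. The titer-change and progression-free survival models were not simulated; the argument carries over, the figures do not.

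**The case against.** The strongest reply is that the objective asks only whether titers correlate with outcome. A prognostic marker need not be separated from its causes, and the analysis is unpowered work in a feasibility study. That stands as a reason for low priority and for keeping the planned model. It does not dispose of the point: hypothesis 2.1.5 lists type and serology as separate measures, and a marker claim invites the question of what serology adds to typing.

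A reader might go further and infer that the titer effects are in fact diluted, that a real effect will usually be missed, and that an own-type analysis should become the main one. The documents do not support this. Section 1.2.3 speaks of type-specific epitopes and relates titers to disease status and grade. It does not say that a titer matters only when the cancer carries that type. If the HPV-16 titer acts in all women, the own-type model has power of about 0.34, against 0.76 to 0.83 as planned. Its apparent advantage when the effect is type-matched (0.62 against 0.23) is also generous. The pooled model assumes equal slopes for the two types, and HPV-16 women alone give about 0.48. Appendix XI treats samples below the 1:100 threshold as seronegative; with an illustrative floor on the titers the contrast shrinks to 0.40 against 0.25.

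Two further objections stand in part. The proxy effect is small under mild assumptions, as the table shows. And cervical swab type is an imperfect marker of tumour type: a swab may carry several types, and specimens negative for beta-globin are excluded.

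**Conclusion.** The point holds as a risk of confounding by HPV type on the protocol's own premises. As written, section 11.1 cannot distinguish a titer association from a tumour-type association. With a strong type effect (OR 0.33) the planned HPV-16 test rejects a true null about two to four times as often as the adjusted one (12% to 25% against 6% to 7%). With OR 0.5 and a 4-fold shift the excess is 2 to 3 percentage points. The type effect, titer shift, titer spread and failure rate are all assumptions, and the type shares are borrowed from HIV-uninfected women.

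Dilution is possible but conditional, and should not be stated as a fact. The point does not touch the primary outcome or safety. It is a cheap improvement to an exploratory analysis, of low priority.

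**What to change.** In section 11.1, add the following:

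1. Each HPV-16 and HPV-18 titer model, and each titer-change model, is reported twice: as planned, and with baseline cervical HPV type (16, 18, other) as a covariate. State a convention for women positive for both types, and how untyped swabs are handled.
2. A titer is described as adding information beyond HPV type only on the basis of the adjusted model.
3. An own-type analysis in women positive for HPV 16 or HPV 18 may be given as supportive only.

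The cost is wording, since type and titer are already collected at baseline; no visit or sample changes. Each adjusted model carries two extra parameters on about 15 failures (0.40 × 38). About three of those are expected in the HPV-18 group (0.40 × 7.6), so the type coefficients themselves will be unstable and should not be interpreted. When titer and type are correlated, adjustment gives up some power for a genuine titer effect (about 0.83 to 0.72); when they are unrelated the loss is about nil. Because swab type only approximates tumour type, some confounding may remain after adjustment, and the report should say so.

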APPENDIX XII: RADIATION THERAPY QUALITY ASSURANCE PROCESS

External Beam Therapy

A. Machine QA: all of the following are required:

- 1) Participation in the annual mailed OSLD/TLD program conducted by the IROC Houston QA Center for an independent basic check of the machine output.
- 2) Submission of machine output calibration as per AAPM TG-51 protocol or IAEA TRS 277 or 398 protocols.
- 3) Provide standards lab (SSDL or ADCL) calibration certificates for the ion chamber and electrometer used in the calibration of the reference beam output for the external beam RT.

B. External Beam Treatment Plan

Submission of a complete treatment plan (to include treatment plan summary, beam-on times, isodose lines, dose volume histograms, beams eye views (BEV), daily treatment record), and completed on-line external beam dosimetry form found on the IROC Houston QA Center website (<http://irochouston.mdanderson.org>) under forms shall be submitted for review by the IROC Houston QA Center and protocol PI. This review verifies that the dose reported is that required by the protocol, no data entry errors have occurred in the calculation, and that there are no transcription and/or reporting errors. The IROC Houston QA Center's participant review may require the participating site to submit additional dosimetry data, as specified by the IROC Houston QA Center, for the therapy machine used to treat the participant if a dose delivery discrepancy is determined.

Brachytherapy

A. Machine QA: all of the following are required:

- b. Submit sample brachytherapy source assay document plus a copy of manufacturer source certificate.
- c. Submit copies of standards lab (SSDL or ADCL) calibration certificates for brachytherapy chamber and electrometer used in source assay.

B. Brachytherapy Treatment Plan

Submission of a complete treatment plan to include source strength, for LDR: source loading and total time, for HDR: dwell positions and dwell times, orthogonal AP and lateral films with magnification factors, and completed on-line Gynecological Brachytherapy Protocol Compliance form found on the IROC Houston QA Center website (<http://irochouston.mdanderson.org>) under forms shall be submitted for review by the IROC Houston QA Center and protocol PI. This review verifies that the dose reported is that required by the protocol, no data entry errors have occurred in the calculation, and that there are no transcription and/or reporting errors. If a dose delivery discrepancy is determined, the IROC Houston QA Center's participant review may require the participating site to submit

additional brachytherapy dosimetry data that was used to treat the participant, as specified by the IROC Houston QA Center.
